4.1 Inclusion Criteria

1. Histologically confirmed diagnosis of gastric and GEJ adenocarcinoma
2. Measurable or non-measurable disease by Response Evaluation Criteria in Solid Tumors (RECIST) 1.1. Stage IV or recurrent disease is required. An irradiated lesion is considered evaluable only if it has shown enlargement since the completion of last radiation.
3. Patients must have received and progressed with prior therapy. Prior therapy with ramucirumab is not allowed. Patients must have recovered from the toxic effects of the previous anti-cancer chemotherapy (with the exception of alopecia).
4. ECOG Performance Score 0 or 1
5. Estimated life expectancy > 3 months
6. Adequate bone marrow, liver and renal function as assessed by the following:
 - o Hemoglobin > 8.0 g/dl
 - o Absolute neutrophil count (ANC) > 1,000/mm³ independent of growth factor support
 - o Platelet count > 100,000/mm³
 - o Total bilirubin < 1.5 times ULN unless bilirubin rise is due to Gilbert's syndrome or of non-hepatic origin
 - o AST, ALT and Alkaline Phosphatase \leq 2.5 times the ULN (\leq 5 x ULN for patients with liver involvement)
 - o Creatinine clearance \geq 30 ml/min
7. Patients must not have had chemotherapy, major surgery, monoclonal antibody therapy or experimental therapy within the 28 days prior to the start of TAS 102 administration.
8. Women of childbearing potential must have a negative serum pregnancy test performed within 7 days prior to the start of study drug. Post-menopausal women (defined as no menses for at least 1 year) and surgically sterilized women are not required to undergo a pregnancy test.
9. Subjects (men and women) of childbearing potential must agree to use adequate contraception beginning at the signing of the ICF until at least 4 months for both females and males after the last dose of study drug. The definition of adequate contraception will be based on the judgment of the principal investigator or a designated associate.
10. Subjects must be able to understand and be willing to sign the written informed consent form. A signed informed consent form must be appropriately obtained prior to the conduct of any trial-specific procedure. Subjects must be willing and able to comply with scheduled visits, treatment schedule, laboratory testing, and other study requirements.

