6.1 Screening First Visit

Screening examinations will only be performed after having received the subject's written informed consent.

The following examinations will be performed within 28 days prior to the first treatment:

- Written subject informed consent to be obtained prior to any screening assessments.
- Complete medical history and physical examination, including demographics, surgery, therapies, medications, smoking, alcohol history, co-existing diseases, allergies, NYHA classification, vital signs (heart rate, respiration rate, temperature, and BP), weight and review of systems.
- Baseline toxicities / AEs
- ECOG Performance Status Assessment
- 12-lead ECG
- Radiologic assessment: CT scan or MRI with tumor measurement and disease assessment of non-measurable disease
- Coagulation (PT-INR and aPTT)
- Hematology (hemoglobin, HCT, RBC, WBC count with differential (neutrophils, bands, lymphocytes, monocytes, eosinophils and basophils) and platelet count
- Chemistry (ALT, AST, alkaline phosphatase, total bilirubin, direct bilirubin, lactate dehydrogenase (LDH), creatine kinase, lipase, amylase, glucose, calcium phosphate, magnesium, bicarbonate, sodium, potassium, chloride, creatinine, blood urea nitrogen (BUN), total protein and albumin
- Urinalysis
- Hepatitis and HIV test
- Serum pregnancy test (if applicable)
- Radiologic assessment tests (CT scan or MRI) performed up to 4 weeks prior to

obtaining informed consent can be used for screening purposes.

6.2 Cycle 1 Day 1

- History and assessment to include physical examination, vital signs (heart rate, respiration rate, temperature and BP) and review of systems
- Toxicity/AE assessment
- ECOG Performance Status Assessment
- Hematology (hemoglobin, HCT, RBC, WBC with differential (neutrophils, bands, lymphocytes, monocytes, eosinophils and basophils) and platelet count
- Chemistry (ALT, AST, AP, total bilirubin, direct bilirubin, glucose, calcium, phosphate, magnesium, bicarbonate, sodium, potassium, chloride, creatinine, BUN, total protein and albumin
- Screening hematology, platelet count and chemistry can be used for cycle 1 day 1 if screening tests are done within 5 days of cycle 1 day 1.
- Issue a new diary card (Appendix B)
- Urinalysis

6.3 Cycle 1 Day 15

- Hematology (hemoglobin, HCT, RBC, WBC with differential (neutrophils, bands, lymphocytes, monocytes, eosinophils and basophils) and platelet count

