6.8 Calendar

	Screening within 28 days of C1D1 ^m	Cycle 1 Day 1 ± 3 days and subsequent cycles	Cycle 1 day 15 ± 3 days	Cycle X day 1 ± 5 day	Cycle X day 15 ± 5 day	End of treatment visit ⁿ	Safety follow-up	Survival follow-up
Complete History/Physical^a	X							
History & Assessment^b		X	X	X		X	X	
Toxicity Notation		X	X	X		X	X	
ECOG	X	X	X	X		X		
ECG	X							
Tumor Measurement/ Disease Assessment^c	X			X		X		
Hematology^d	X	X	X	X	X	X		
Chemistry^e	X	X	X	X	X	X		
Coagulation^f	X							
Urinalysis^g	X	X		X		X		
24hr urine protein^h			X	X	X	X		
Hepatitis and HIV Screeningⁱ	X							
Serum	X							

Pregnancy, if applicable j								
Survival f/u k								X
Diary – Issued/Retur- ned¹		X		X				

- a. *Complete medical history and physical examination* including demographics, surgery, therapies, medications, smoking, alcohol history, co-existing diseases, allergy, NYHA classification, vital signs (heart rate, respiration rate, temperature and BP), height, weight and review of systems.
- b. *History and assessment* including brief examination, vital signs and review of systems. Note all toxicities and adverse events, using CTCAE version 5.
- c. Tumor assessment using CT or MRI (at investigator's discretion) will be collected at screening, after every 3 cycles, and as clinically indicated. Tumor response will be assessed using RECIST 1.1 criteria. Tumor measurement/disease assessment should be performed within 7 days at the beginning of every 3rd cycle.
- d. Hemoglobin, hematocrit, red blood cell count, white blood cell count with differential (neutrophils, bands, lymphocytes, monocytes, eosinophils and basophils) and platelet count.
- e. ALT, AST, alkaline phosphatase, total bilirubin, direct bilirubin, LDH, creatine kinase, lipase, amylase glucose, calcium, phosphate, magnesium, bicarbonate, sodium, potassium, chloride, creatinine, blood urea nitrogen (BUN), total protein and albumin.
- f. PT-INR and aPTT.
- g. Urinalysis including blood, glucose, protein, specific gravity. If dipstick or routine urinalysis indicates proteinuria $\geq 2+$, a 24-hour urine collection must be obtained in 2 weeks.
- h. If necessary
- i. Hepatitis B surface antigen, surface antibody, core antigen and Hepatitis C antibody
- j. Pregnancy test will be performed at baseline for WOCBP and then only as clinically indicated

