- k. Can be performed over the phone. After off treatment following disease progression, physical assessments (with lab tests performed at the discretion of the treating investigator) should take place every 3 months for up to two years or death.
- l. A diary card will be issued on day 1 of each cycle and the issued diary card will be returned on subsequent cycle
- m. Radiologic tests (CT scan or MRI) performed up to 4 weeks prior to obtaining informed consent can be used for screening purposes.

- n. Restaging imaging only to be performed if not done within the last 4 weeks

7. Assessment types

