7.1 Pre-Treatment Assessments

The nature of the study and the associated potential risks will be explained to all study candidates and a signed informed consent must be obtained before any study-specific Pre-Treatment procedures are performed. Pre-Treatment assessments must be completed and reviewed within 21 days prior to the start of study drug treatment to ensure eligibility for study entry

Pre-Treatment evaluations will include inclusion/exclusion criteria evaluation, demographic data collection, ECOG performance status, NYHA classification, medical and surgical history collection, vital signs, complete physical examination (including height and weight), 12-lead ECG, biochemistry, hematology and urinalysis, pregnancy test (urine or serum β - hCG in women of childbearing potential only), and tumor assessments

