Target lesions. All measurable lesions up to a maximum of 2 lesions per organ and 5 lesions in total, representative of all involved organs, should be identified as **target lesions** and recorded and measured at baseline. Target lesions should be selected on the basis of their size (lesions with the longest diameter), be representative of all involved organs, but in addition should be those that lend themselves to reproducible repeated measurements. It may be the case that, on occasion, the largest lesion does not lend itself to reproducible measurement in which circumstance the next largest lesion which can be measured reproducibly should be selected. A sum of the diameters (longest for non-nodal lesions, short axis for nodal lesions) for all target lesions will be calculated and reported as the baseline sum diameters. If lymph nodes are to be included in the sum, then only the short axis is added into the sum. The baseline sum diameters will be used as reference to further characterize any objective tumor regression in the measurable dimension of the disease.

Non-target lesions. All other lesions (or sites of disease) including any measurable lesions over and above the 5 target lesions should be identified as **non-target lesions** and should also be recorded at baseline. Measurements of these lesions are not required, but the presence, absence, or in rare cases unequivocal progression of each should be noted throughout follow-up.

Methods for Evaluation of Measurable Disease

All measurements should be taken and recorded in metric notation using a ruler or calipers. All baseline evaluations should be performed as closely as possible to the beginning of treatment and never more than 4 weeks before the beginning of the treatment.

The same method of assessment and the same technique should be used to characterize each identified and reported lesion at baseline and during follow-up. Imaging-based evaluation is preferred to evaluation by clinical examination unless the lesion(s) being followed cannot be imaged but are assessable by clinical exam.

Clinical lesions. Clinical lesions will only be considered measurable when they are superficial (e.g., skin nodules and palpable lymph nodes) and ≥ 10 mm diameter as assessed using calipers (e.g., skin nodules). In the case of skin lesions, documentation by color photography, including a ruler to estimate the size of the lesion, is recommended.

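### The screening-scan allowance counts back from consent, so the RECIST baseline can be up to 56 days old at first dose, against limits of 4 weeks in Appendix A and 21 days in section 7.1

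*Combined protocol and SAP*

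**What the plan says.** Four places govern the age of the pre-treatment scan.

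- **Section 6.1, opening and last bullet.** "The following examinations will be performed within 28 days prior to the first treatment"; written consent is the first item listed and must precede screening assessments. The last bullet then admits existing imaging: "Radiologic assessment tests (CT scan or MRI) performed up to 4 weeks prior to" consent may serve for screening.
- **Section 6.8, calendar.** The column headed "Screening within 28 days of C1D1" carries footnote m, which reads: "Radiologic tests (CT scan or MRI) performed up to 4 weeks prior to obtaining informed consent can be used for screening purposes".
- **Section 7.1.** "Pre-Treatment assessments must be completed and reviewed within 21 days prior to the start of study drug treatment". The list that follows includes tumor assessments.
- **Appendix A, methods for measurable disease.** Baseline evaluations are to be as close as possible to the start of treatment and "never more than 4 weeks before the beginning of the treatment".

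Footnote c of the calendar says that imaging "will be collected at screening, after every 3 cycles, and as clinically indicated". The calendar has no tumor measurement at Cycle 1 Day 1. Inclusion item 7 bars chemotherapy, major surgery, antibody therapy and experimental therapy "within the 28 days prior to the start of TAS 102 administration".

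**The concern.** The allowance for existing scans is tied to consent, whereas Appendix A and section 7.1 tie the baseline to the start of treatment. A site can follow footnote m exactly and still breach both. Because the screening scan is the only one scheduled before dosing, it supplies the baseline sum of diameters.

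Under Appendix A, partial response is judged against that baseline sum, progression against the smallest sum on study (baseline included), and a new lesion counts as progression. PFS runs from the start of treatment, not from the scan. Eligible patients have progressed on earlier therapy, so growth between scan and first dose is the likely direction. Such growth would mask some true responses and bring some progression dates forward.

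The 28-day limit also has a specific role here. A scan inside the 28-day washout of item 7 necessarily follows the treatments listed there. A scan from days -56 to -29 can predate the end of prior systemic therapy, and change from baseline would then mix earlier treatment, washout and study treatment.

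**Working it through.** The plan gives no computed figure for scan age. Its only computed design figure, 25 evaluable patients (15 + 10, at least 7/15 and at least 15/25), reproduces as a Simon minimax design: type I error 0.0951 at 0.45 and power 0.9004 at 0.70. It uses survival status only, so it does not depend on imaging.

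**Step 1: maximum scan age at first dose.** Scan age = (scan to consent) + (consent to first dose).

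- Sections 6.1 and 6.8: 28 + 28 = 56 days.
- If section 7.1's 21 days is taken to bound consent: 28 + 21 = 49 days.
- Appendix A: 28 days.
- Section 7.1 applied to the scan itself: 21 days.

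The permitted maximum exceeds Appendix A by 56 - 28 = 28 days.

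**Step 2: effect of growth before dosing.** Let g be the proportional growth in the sum of diameters between scan and first dose.

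- True shrinkage from first-dose size needed for partial response (a 30% fall from baseline): 1 - 0.7/(1 + g).
- True growth from first-dose size at which the 20% progression threshold is met, when baseline is the smallest sum: 1.2/(1 + g) - 1. The 5 mm absolute increase is also required.

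**Step 3: a value for g.** The documents give no growth rate, so this is an assumption. With volume doubling time V days and diameter proportional to the cube root of volume, g = 2^(days/(3V)) - 1. The fair comparison is a 56-day-old scan with a 28-day-old one, because Appendix A permits the latter.

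| Assumed V (days) | g at 28 d | g at 56 d | PR shrinkage needed, 28 d | PR shrinkage needed, 56 d | Difference (points) |
|---|---|---|---|---|---|
| 45 | 15.5% | 33.3% | 39.4% | 47.5% | 8.1 |
| 60 | 11.4% | 24.1% | 37.2% | 43.6% | 6.4 |
| 90 | 7.5% | 15.5% | 34.9% | 39.4% | 4.5 |
| 120 | 5.5% | 11.4% | 33.7% | 37.2% | 3.5 |

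For progression from baseline, V = 90 gives a true-growth threshold of 11.7% with a 28-day-old scan and 3.9% with a 56-day-old scan; V = 120 gives 13.7% and 7.7%. The relative threshold is already reached at first dose when V is about 71 days or less with a 56-day-old scan, and about 35 days or less with a 28-day-old scan.

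**The case against.** The strongest reply is that the allowance does less than it seems. Section 6.1 wants consent before screening procedures, so the natural purpose of footnote m is to let existing standard-of-care scans count without waiving the 28-day heading of its column. The words on screening purposes could also mean eligibility only, leaving the baseline to Appendix A. That reading is possible, and it means the defect is an unresolved conflict rather than a settled 8-week baseline. It does not remove the conflict: no second baseline scan is scheduled, nothing requires an old scan to be repeated, and nothing says that Appendix A overrides the allowance.

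Several limits on the effect stand in full.

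- A reader might set an old scan against no pre-dose growth at all: with 10% growth, partial response at 36.4% instead of 30% and progression at 9.1% instead of 20%. That overstates the defect, since a compliant 28-day-old scan carries growth too.
- Once the sum falls below baseline on study, the old baseline no longer sets the progression threshold.
- The direction is probable, not certain. Item 7 does not list radiotherapy, and exclusion 20 restricts radiotherapy to target lesions only within 2 weeks of enrollment. Irradiation after an old scan could shrink lesions before dosing and favour response.
- Exclusion 18 counts 4 weeks for chemotherapy from enrollment, whose date is not defined. If enrollment is dated at consent, prior chemotherapy would usually have ended before even the oldest permitted scan; if it is dated nearer first dose, it need not have.
- ORR applies only to patients with measurable disease, while non-measurable disease is also eligible.

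**Conclusion.** The inconsistency is real: sections 6.1 and 6.8 permit a baseline scan up to 56 days before first dose (49 if section 7.1 bounds consent), against 28 days in Appendix A and 21 days in section 7.1. Fifty-six days is the permitted maximum, and the documents say nothing about the typical gap.

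The probable consequence is an ORR biased downward and progression called early in some patients. Relative to a 28-day-old scan, the shrinkage needed for a partial response rises by about 4.5 points at an assumed doubling time of 90 days and 3.5 points at 120; faster growth (45 to 60 days) would give 6 to 8 points. These figures rest on steady growth and on a scan at the extreme of the window. The progression effect applies only where baseline is the smallest sum and the 5 mm rule is met.

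A reader might infer that the efficacy conclusion is compromised. The documents do not support that: 6-month overall survival, the 7/15 and 15/25 rules and the sample size of 25 do not use imaging, and ORR and PFS are secondary endpoints reported with confidence intervals and no stated test. The point merits a correction to the text, not a change of design.

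**What to change.** Reconcile section 6.1 (opening and last bullet), footnote m of section 6.8, section 7.1 and Appendix A to one limit counted back from Cycle 1 Day 1. For example, replace the last bullet of 6.1 and footnote m with: *A standard-of-care scan done before consent may be used as baseline if performed within 28 days before Cycle 1 Day 1; otherwise repeat it.* Align section 7.1's window for tumor assessments with the same limit; otherwise its 21 days would still conflict.

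The cost is a few sentences, plus a current scan for the few patients whose imaging is too old or whose first dose slips. Those patients already fall outside Appendix A, so this adds no requirement that the plan does not contain. Existing scans within the limit remain usable.

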7.1 Pre-Treatment Assessments

The nature of the study and the associated potential risks will be explained to all study candidates and a signed informed consent must be obtained before any study-specific Pre-Treatment procedures are performed. Pre-Treatment assessments must be completed and reviewed within 21 days prior to the start of study drug treatment to ensure eligibility for study entry

Pre-Treatment evaluations will include inclusion/exclusion criteria evaluation, demographic data collection, ECOG performance status, NYHA classification, medical and surgical history collection, vital signs, complete physical examination (including height and weight), 12-lead ECG, biochemistry, hematology and urinalysis, pregnancy test (urine or serum β - hCG in women of childbearing potential only), and tumor assessments

7.2 Efficacy

Response and progression will be evaluated using the international criteria proposed by the revised Response Evaluation Criteria in Solid Tumors (RECIST) guideline (version 1.1) (see Appendix A). Changes in the largest diameter (unidimensional measurement) of the tumor lesions and the shortest diameter in the case of malignant lymph nodes are used in the RECIST criteria.

7.3 Safety

Safety assessments will consist of monitoring and recording all adverse events, including serious adverse events, the monitoring of hematology, blood chemistry, ECG and the regular monitoring of vital signs, and physical condition as shown in corresponding tables.

8. Safety monitoring and reporting

8.1 Adverse Events

8.1.1 Definitions

A serious adverse event is an undesirable sign, symptom or medical condition which:

1. Is fatal or life-threatening.
2. Requires or prolongs hospitalization.
3. Results in persistent or significant disability/incapacity.
4. Constitutes a congenital anomaly or a birth defect.
5. Is medically significant, may jeopardize the subject and may require medical or surgical

intervention to prevent one of the outcomes listed above.

Information about all adverse events, whether volunteered by the subject, discovered by investigator questioning, or detected through physical examination, laboratory test or other means, will be collected and recorded and followed as appropriate. An adverse event is any undesirable sign, symptom or medical condition occurring after starting study treatment.

Medical conditions/diseases present before starting study treatment are only considered adverse events if they worsen after starting study treatment. Abnormal laboratory values or test results constitute adverse events only if they induce clinical signs or symptoms or require therapy.

Full information from serious adverse events as well as adverse events concerning medication errors and overdose will be reported to Taiho Drug Safety or Designee. **This can be performed by faxing it to Taiho or designee at [contact] or via e-mail at [contact] (please note the underscore between '102' and 'Safety').**

In addition to the above, fatal events will also be documented by a separate death form, instead of reporting them as AE CTCAE grade.

Events not considered to be serious adverse events are hospitalizations for the:

- Routine treatment or monitoring of the studied indication, not associated with any deterioration in condition.
- Treatment, which was elective or pre-planned, for a pre-existing condition that did not worsen.
- Treatment on an emergency, outpatient basis for an event not fulfilling any of the definitions of serious given above and not resulting in hospital admission.

Pregnancy, although not itself a serious adverse event, should also be reported on a serious adverse event form or pregnancy form and be followed up to determine outcome, including spontaneous or voluntary termination, details of birth, and the presence or absence of any birth defects or congenital abnormalities.

Only the serious adverse event occurring after the patient has started taking the study medication, and until 4 weeks after the patient has stopped study participation must be reported. The period after discontinuing study drug may be extended if there is a strong suspicion that the drug has not yet been eliminated.

Progression of the cancer under study is not considered an adverse event.

